2.0 Goals

2.1 Primary Objective:

To estimate and compare treatment failure-free rate at 40 weeks from randomization of patients with unresectable/metastatic clear cell Renal Cell Carcinoma (ccRCC) receiving one of the following regimens:

- Arm A: Pazopanib 800mg daily plus intravenous (IV) ascorbic acid 1g/kg 3 times/week.
- Arm B: Pazopanib 800mg daily

2.2 Secondary Objective:

- 2.21 To estimate and compare the overall survival (OS) in patients receiving pazopanib with or without IV ascorbic acid
- 2.22 To estimate and compare the progression-free survival (PFS) in patients receiving pazopanib with or without IV ascorbic acid
- 2.23 To estimate and compare the overall response rate (ORR) in patients receiving pazopanib with or without IV ascorbic acid
- 2.24 To estimate and compare the duration on pazopanib treatment in patients receiving pazopanib with or without IV ascorbic acid
- 2.25 To assess the adverse events (AE) profile and safety of each treatment arm using the CTCAE

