10.3 Assessment of Attribution

When assessing whether an adverse event is related to a medical treatment or procedure, the following attribution categories are utilized:

- Definite - The adverse event *is clearly related* to the agent(s).
- Probable - The adverse event *is likely related* to the agent(s).
- Possible - The adverse event *may be related* to the agent(s).
- Unlikely - The adverse event *is doubtfully related* to the agent(s).
- Unrelated - The adverse event *is clearly NOT related* to the agent(s).

Events determined to be possibly, probably or definitely attributed to a medical treatment suggest there is evidence to indicate a causal relationship between the drug/device and the adverse event.

10.4 Expedited Reporting Requirements for Studies using Commercial Agent(s) ONLY:

Expedited Reporting Requirements for Adverse Events that Occur in a Non-IND/IDE trial within 30 Days of the Last Administration of a Commercial Agent^{1,2}**FDA REPORTING REQUIREMENTS FOR SERIOUS ADVERSE EVENTS (21 CFR Part 312)**

NOTE: Investigators **MUST** immediately report to the sponsor **ANY** Serious Adverse Events, whether or not they are considered related to the investigational agent(s)/intervention (21 CFR 312.64)

An adverse event is considered serious if it results in **ANY** of the following outcomes:

- 1) Death
- 2) A life-threatening adverse event
- 3) An adverse event that results in inpatient hospitalization or prolongation of existing hospitalization for \geq 24 hours
- 4) A persistent or significant incapacity or substantial disruption of the ability to conduct normal life functions
- 5) A congenital anomaly/birth defect.
- 6) Important Medical Events (IME) that may not result in death, be life threatening, or require hospitalization may be considered serious when, based upon medical judgment, they may jeopardize the patient or subject and may require medical or surgical intervention to prevent one of the outcomes listed in this definition. (FDA, 21 CFR 312.32; ICH E2A and ICH E6).

ALL SERIOUS adverse events that meet the above criteria **MUST** be immediately reported to the sponsor within the timeframes detailed in the table below.

Hospitalization	Grade 1 Timeframes	Grade 2 Timeframes	Grade 3 Timeframes	Grade 4 & 5 Timeframes
Resulting in Hospitalization \geq 24 hrs	7 Calendar Days			24-Hour 3 Calendar Days
Not resulting in Hospitalization \geq 24 hrs	Not required		7 Calendar Days	

Expedited AE reporting timelines are defined as:

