10.53 Baseline and Adverse Events Evaluations

The following pre-treatment symptoms/conditions are to be graded at baseline and adverse events are to be graded at each evaluation using CTCAE v4.0 grading. If CTCAE v4.0 grading is not used, note the grading scale used in the table below

System Organ Class (SOC)	Adverse event/Symptoms	Baseline	Each evaluation
General Disorders	Fatigue	X	X
Gastrointestinal Disorders	Nausea	X	X
	Diarrhea	# of stools	X
	Mucositis oral	X	X
Injury, poisoning and procedural complications	Vascular access complication		X
Infections and infestations	Catheter related infection		X
Investigations	Blood bilirubin increased	X	X
	Aspartate aminotransferase increased	X	X
	Alanine aminotransferase increased	X	X
	Creatinine increased	X	X

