16.32 Definitions and Analyses of Secondary Endpoints

16.321 Overall Survival

Survival time is defined as the time from randomization to death due to any cause. Patients who are alive will be censored for death at the time of last known alive. All patients meeting the eligibility criteria that have signed a consent form and begun treatment will be considered evaluable for estimation of the survival distribution. The distribution of survival time will be estimated using the method of Kaplan-Meier and be compared using log rank tests.

16.322 Progression Free Survival

Progression Free Survival is defined as the time from start of study therapy to documentation of disease progression or death, whichever comes first. Patients who are still alive and have not progressed will be censored for progression at the time of the last tumor assessment. All patients meeting the eligibility criteria that have signed a consent form and begun treatment will be considered evaluable for estimation of the survival distribution. The progression free survival distribution will be estimated using the Kaplan-Meier method.

16.323 Overall Response Rate

A tumor response is defined to be a CR or PR noted as the objective response (according to RECIST v. 1.1) All patients meeting the eligibility criteria who have signed a consent form and have begun treatment will be evaluable for response. The best objective response rates between the two arms will be compared using a Chi-Square test.

16.324 Duration of time on pazopanib

Duration of time on pazopanib is defined as the time from initial dose of

pazopanib until the date the patient is considered off-treatment for pazopanib or death, whichever comes first. Only patients received at least 1 dose of pazopanib will be considered evaluable for this analysis. The time on pazopanib will be described using descriptive statistics.

16.325 Adverse events:

As per NCI CTCAE version 4.0, the term toxicity is defined as adverse events that are classified as either “possibly,” “probably,” or “definitely related” to study treatment. The maximum grade for each type of toxicity will be recorded for each patient, and frequency tables will be reviewed to determine toxicity patterns within patient groups. In addition, we will review all adverse event data that is graded as 3, 4, or 5 and classified as either “unrelated” or “unlikely to be related” to study treatment in the event of an actual relationship developing.

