Adverse events and toxicities will be evaluated using all patients who have received any study treatment as well as summarizing those who have been included in the efficacy analyses. The overall adverse event rates for grade 3 or higher adverse events will be compared using Chi-Square tests between the 2 treatment arms.

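### Section 16.325 tabulates low-grade adverse events only when judged related, so grade 1-2 solicited events judged unlikely or unrelated reach no specified table in this open-label trial

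*Combined protocol and SAP*

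**What the plan says.** Objective 2.25 is "To assess the adverse events (AE) profile and safety of each treatment arm using the CTCAE". It is not limited to related events.

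Section 10.3 gives five attribution categories, from definite to unrelated. Section 16.325 then narrows the vocabulary: "the term toxicity is defined as adverse events that are classified as either" possible, probable or definite. On that narrowed term it builds its tables by type: "The maximum grade for each type of toxicity will be recorded for each patient", followed by frequency tables. For the two remaining categories it adds only this: "we will review all adverse event data that is graded as 3, 4, or 5 and classified as either" unrelated or unlikely.

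The section closes with two further statements. One sets the population: "Adverse events and toxicities will be evaluated using all patients who have received any study treatment". The other is the only between-arm test: "The overall adverse event rates for grade 3 or higher adverse events will be compared using Chi-Square tests between the 2 treatment arms". It states no attribution limit.

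On the collection side, section 10.53 says that "adverse events are to be graded at each evaluation using CTCAE v4.0 grading". It lists fatigue, nausea, diarrhea, oral mucositis, vascular access complication, catheter related infection, bilirubin, AST, ALT and creatinine. It sets no minimum grade and no attribution limit. Section 18.1 has a solicited-event form submitted at each evaluation during treatment and at its end.

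**The concern.** The plan asks sites to grade ten events at every evaluation whatever their cause, then specifies a low-grade table that keeps only those judged related. Section 1.5 describes the trial as open-label, so the judgement can be made with the arm known. The documents do not say who makes it.

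Attribution could plausibly differ by arm. Arm A has two agents to which an event can be attributed and Arm B has one. Fatigue, nausea and diarrhea are listed for both drugs (15.17 and 15.27). Renal failure is listed for high-dose ascorbic acid in 15.27, while 15.17 does not list a creatinine rise for pazopanib, although 8.12 does have a creatinine rule for it. A mild creatinine rise might be called related in Arm A and unlikely in Arm B, and so disappear from the Arm B table.

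At stake is the low-grade part of objective 2.25, and the first hypothesis in 1.4, which expects better tolerance with the combination. Low-grade fatigue, nausea and diarrhea bear directly on tolerance.

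**Working it through.** The plan gives no figure to reproduce here. The check is a comparison of what is collected with what is reported.

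**1. Outputs named in 16.325, by grade and attribution**

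- Related, grade 1-2: maximum-grade table.
- Related, grade 3-5: maximum-grade table and chi-square test.
- Unlikely or unrelated, grade 3-5: review and chi-square test.
- Unlikely or unrelated, grade 1-2: no table, review or test.

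**2. Is the empty cell collected?** For the ten events in 10.53, yes. The grade and attribution limits in 10.54 apply only to events not already specified in 10.5, so they do not remove solicited events. For unsolicited events, 10.54 asks for grade 2 only if at least possibly related and does not ask for grade 1. The point is therefore confined to the ten solicited events. Eight of them have a baseline entry (diarrhea as a stool count); vascular access complication and catheter related infection do not.

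**3. What differential attribution would do.** Suppose the true any-cause grade 1-2 rate of an event is r in both arms, and the shares judged related are a(A) and a(B). Then

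tabulated difference = r × [a(A) − a(B)].

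The documents give none of these quantities. The values below are assumptions for illustration only.

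- r = 0.40, shares 0.90 and 0.90: 0.36 − 0.36 = 0.
- r = 0.40, shares 0.90 and 0.70: 0.36 − 0.28 = 8 points.
- r = 0.60, shares 0.90 and 0.50: 0.54 − 0.30 = 24 points.
- r = 0.60, shares 0.50 and 0.90: 0.30 − 0.54 = −24 points.

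With r from 20% to 60%, a(A) fixed at 90% and a(B) from 50% to 90%, the spurious difference runs from 0 to 24 points. Reversing the shares reverses the sign.

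**4. Would an all-attribution table be comparable for the laboratory events?** Not fully, for two reasons.

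- Draw frequency (section 4.0, footnote 4). Arm A has weekly draws in cycle 1 and two per cycle afterwards: 4 + 9 × 2 = 22. Arm B has one per cycle: 10 × 1 = 10. This assumes that all ten cycles are completed and that weekly means four draws in cycle 1. Baseline and end-of-treatment draws are not counted.
- Assay interference (section 15.26). Ascorbic acid can produce falsely negative bilirubin results during an infusion or in the 24 hours after it. Arm A is infused three times a week, and section 4.0 does not time chemistry draws relative to infusions.

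**The case against.** The strongest reply is that the closing paragraph of 16.325 names adverse events separately from toxicities, directly after toxicity has been defined as related events. With objective 2.25, that signals an intent to look past the attribution filter. Section 16.41 also gives the monitoring board safety data at least twice a year with no grade or attribution limit stated. Nothing in the plan forbids an all-cause table. The plan also guards against misattribution where it matters most: it reviews unrelated and unlikely events at grade 3-5 in case a relationship emerges, and tests grade 3 or higher with no attribution limit stated.

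The visible intent stands, and it keeps the point small. But the closing sentence fixes a population and names no table, and the content of the board reports is unspecified. Neither supplies the low-grade table. The grade 3-5 review accepts that attribution can be wrong, but applies that caution only at high grade.

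It is also fair that the fix does not yield an unbiased comparison. Symptoms remain subject to open-label reporting, and the laboratory rows carry the limits described above.

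A reader might infer that the low-grade safety comparison is biased, or that safety data are lost. The documents support neither. They contain no attribution rates from which to show a bias, and the forms collect the events.

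**Conclusion.** The point holds as a minor one. Grade 1-2 events solicited under 10.53 and judged unlikely or unrelated are collected but reach no specified table. The only low-grade table that is specified depends on a judgement that can be made knowing the arm. A between-arm difference in it can therefore reflect attribution, occurrence or both. The size cannot be estimated from the documents and may be nil; the 0 to 24 points above follow wholly from assumed rates.

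A reader might extend this to the main safety comparison or to efficacy. That does not follow. The grade 3 or higher test carries no stated attribution limit, and the primary endpoint does not draw on these tables. The stopping rules in 16.42 concern grade 4 and 5 events, so the low-grade gap does not touch them. They do use the same relatedness filter, but that is a separate matter.

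**What to change.** Add to 16.325:

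> For each event solicited in 10.53, the maximum on-treatment grade (and worsening from baseline where a baseline grade exists) will be tabulated by arm for all treated patients regardless of attribution; attributed events will be shown in a second table.

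Footnote the laboratory rows with two facts. Chemistry is scheduled more often in Arm A (about 22 v 10 on-treatment draws, under the assumptions above). Arm A bilirubin may be falsely low if drawn during an infusion or within 24 hours after it (15.26).

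A sensitivity table limited to draws scheduled in both arms is optional. It should not be the only between-arm laboratory table: under 8.21 an Arm A creatinine rise is managed with hydration and a reduced or held dose, and could have resolved by the next shared draw. It would need the laboratory form, because footnote 6 of section 4.0 records adverse events by cycle.

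The cost is one sentence, one footnote and one or two tables from forms already submitted. The downsides are that background disease events enter both arms, open-label reporting bias remains, and vascular access and catheter events stay descriptive because Arm B has no protocol infusion.

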10.54 Case Report Forms - Academic and Community Cancer Research United (ACCRU)

Submit the following AEs not specified in Section 10.5 (paper or electronic, as applicable)

10.541 Grade 2 AEs deemed *possibly, probably, or definitely* related to the study treatment or procedure.

10.542 Grade 3 and 4 AEs regardless of attribution to the study treatment or procedure.

10.543 Grade 5 AEs (Deaths)

10.5431 Any death within 30 days of the patient’s last study treatment or procedure regardless of attribution to the study treatment or procedure.

10.5432 Any death more than 30 days after the patient’s last study treatment or procedure that is felt to be at least possibly treatment related must also be submitted as a Grade 5 AE, with a CTCAE type and attribution assigned.

- 10.55 Refer to the instructions in the Case Report Forms (CRF) Packet (or electronic data entry screens, as applicable) regarding the submission of late occurring AEs following completion of the Active Monitoring Phase (i.e., compliance with Test Schedule in Section 4.0).

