13.0 Treatment/Follow-up Decision at Evaluation of Patient

13.1 Patients who are CR, PR, or SD will continue treatment per protocol up to a maximum of 10 cycles or until PD whichever is first. After 10 cycles of treatment, treatment may be continued off study per physician discretion. Patients who are CR, PR, or SD after 10 cycles will move to Observation Phase of the trial (see section 13.2).

13.2 Observation:

Patients who complete protocol treatment, or discontinue protocol treatment due to unacceptable toxicity or other complicating disease, will be followed every 8 weeks (+/- 7 days) for a maximum of 2 years from the registration in the Observation Phase per Section 4.0 of the protocol.

13.3 Event Monitoring:

Patients who develop PD, choose alternative therapy, refuse treatment or refuse to be followed in observation at any time will go to the Event Monitoring phase and be followed every 6 months (+/- 30 days) for a maximum of 3 years from registration per Section 18.0 of the protocol. Treatment options for these patients are at the discretion of the treating physician.

13.4 Patients who develop PD in the CNS only should receive whole brain radiotherapy (WBRT) and continue treatment on study after completion of WBRT.

13.5 A patient is deemed *ineligible* if after registration, it is determined that at the time of registration, the patient did not satisfy each and every eligibility criteria for study entry. The patient may continue treatment off-protocol at the discretion of the physician as long as there are no safety concerns, and the patient was properly registered. The patient will go directly to the event-monitoring phase of the study (or off study, if applicable).

- If the patient received treatment, all data up until the point of confirmation of ineligibility must be submitted. Event monitoring will be required per Section 18.0 of the protocol.
- If the patient never received treatment, on-study material must be submitted. On-study material and the Off Treatment Form must be submitted. No further data submission is necessary.

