16.2 Statistical Design

16.21 Sample Size and Power:

Based on a study conducted by Motzer et. al, the median duration of pazopanib treatment was 8 month which is approximately equal to a TFF40 rate of 45%. A total of 82 eligible patients (41 in the IV ascorbic acid plus Pazopanib arm and 41 in the Pazopanib only arm) will provide 81% power to detect a 19% increase of TFF40 from 45% (in Pazopanib only arm) to 64% (in the IV ascorbic acid plus Pazopanib arm) assuming a one-sided type I error rate of 0.19 (EAST 6.4). We anticipate accruing an additional 9 patients to account for ineligibility, cancellations, and major violation for a maximum sample size of 91 patients.

16.22 Accrual Time and Study Duration:

The anticipated accrual rate is approximately 5 patients per month. Therefore, the accrual period for this randomized phase II study is expected to be 18.2. The final analysis can begin approximately 27.7 months after the trial is activated, i.e. as soon as the last patient has been observed for 40 weeks.

16.23 Operating Characteristics:

This randomized phase II design has a significance level of 0.19 when the true success proportion is 45%, and a power of 81% for detecting a true success proportion of 64%, assuming that the number of successes is binomially distributed. The probability of declaring that this regimen warrants further study (i.e. statistical power) under various success proportions can be tabulated as a function of the true success proportion as follows:

True TFF40 rate †		%‡ of times that Pazopanib+IV ascorbic acid is superior at the final analysis
Pazopanib only	Pazopanib+IV ascorbic acid	
45%	45%	18.34
45%	55%	47.93
45%	64%	79.45

‡ Proportions are based on 10,000 replicates in the simulation study

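### The planned comparison of grade 3 or higher adverse events takes no account of time at risk, which would be longer in Arm A if ascorbic acid works; a rate per patient-month should be added

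*Combined protocol and SAP*

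**What the plan says.** Section 16.325 defines the safety comparison: "The overall adverse event rates for grade 3 or higher adverse events will be compared using Chi-Square tests between the 2 treatment arms". The population is broad: "Adverse events and toxicities will be evaluated using all patients who have received any study treatment". For the toxicity tables, "The maximum grade for each type of toxicity will be recorded for each patient". I read the chi-square as comparing the proportions of patients with at least one grade 3 or higher event. The section names no time window, person-time, time-to-event method or significance level.

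Time under observation is set elsewhere:

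- **On treatment.** Section 13.1 continues treatment until progression, for at most 10 cycles of 28 days (40 weeks). The section 4.0 test schedule assesses adverse events each cycle and at the end of treatment.
- **After progression, alternative therapy or refusal.** Under section 13.3 these patients "will go to the Event Monitoring phase and be followed every 6 months". Section 18.1 lists only the late adverse event form for them, if applicable.
- **After completing treatment or stopping for toxicity.** Section 13.2 sends these patients to observation every 8 weeks, up to 2 years from registration. The test schedule marks adverse event assessment there, while section 18.1 again lists only the late form.

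Section 16.324 summarises time on pazopanib descriptively and does not link it to the adverse event test.

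**The concern.** A patient who has not failed stays longer under cycle-by-cycle assessment and has more time in which to have a first severe event. Section 1.4 hypothesises longer duration on therapy in Arm A, and section 16.21 powers the trial on fewer treatment failures there. The trial therefore hopes to produce unequal exposure, and the only planned between-arm test for objective 2.25 (the safety profile of each arm) ignores it.

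The effect is not specific to one kind of event and would remain if both arms had identical visit schedules. At stake is the benefit-risk statement after a positive primary result: part of any Arm A excess could reflect longer observation, and no planned analysis would separate that from a higher event rate.

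**Working it through.** **1. The plan's own figures.** Section 16.21 equates a median of 8 months on pazopanib with 45% failure-free at 40 weeks. With exponential times and 40 weeks = 9.2 months, 0.5^(9.2/8) = 0.451, which agrees. For power, the unpooled standard error at 41 per arm is √(0.45×0.55/41 + 0.64×0.36/41) = 0.108, and 0.19/0.108 = 1.76. With one-sided alpha 0.19 (critical value 0.878), power is Φ(1.76 − 0.878) = 81.1%, against the stated 81%.

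**2. Time at risk.** Take exponential treatment failure as a proxy for the end of time at risk, capped at 40 weeks.

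- Arm B: λ = −ln(0.45)/9.2 = 0.0868 per month; mean time (1 − 0.45)/0.0868 = 6.34 months
- Arm A: λ = −ln(0.64)/9.2 = 0.0485 per month; mean time (1 − 0.64)/0.0485 = 7.42 months
- Ratio: 7.42/6.34 = 1.17

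**3. Crude proportion at an identical event hazard.** Let h be the monthly hazard of a first grade 3 or higher event, the same in both arms. The expected proportion with an event by time c is

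P = h/(h+λ) × (1 − exp(−(h+λ)c)).

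The documents give no grade 3 or higher incidence, so Arm B values of 20% to 80% are assumed, and h is solved to match each one. With c = 9.2 months:

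| Arm B | h per month | Arm A | Excess (points) | SE of difference, 41 per arm (points) |
|---|---|---|---|---|
| 20% | 0.036 | 23.2% | 3.2 | 9.1 |
| 30% | 0.059 | 34.6% | 4.6 | 10.3 |
| 50% | 0.123 | 56.8% | 6.8 | 11.0 |
| 70% | 0.242 | 77.5% | 7.5 | 9.7 |
| 80% | 0.374 | 86.7% | 6.7 | 8.2 |

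**4. Sensitivity to the window and to the effect.**

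| Variation | Arm B range | Excess (points) |
|---|---|---|
| Events only in the first 3 months | 30% to 70% | 1.6 to 3.0 |
| Events only in the first 6 months | 30% to 70% | 3.1 to 5.5 |
| On treatment plus 30 days | 20% to 80% | 2.7 to 6.2 |
| True Arm A rate 55%, not 64%, to 40 weeks | 30% to 70% | 2.5 to 4.1 |
| Counted to failure or 104 weeks (upper bound; exposure ratio 1.40) | 20% to 80% | 7.1 to 12.4 |

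**5. Effect on the test.** At an assumed two-sided 0.05 level (the plan states none), the uncorrected chi-square at 41 per arm was enumerated exactly for the 40-week window. It finds Arm A significantly worse in 5.5% to 12.9% of trials, against 2.5% to 3.0% with equal exposure.

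**6. What removes the excess.** Expected time at risk to first event, failure or cap is (1 − exp(−(h+λ)c))/(h+λ), and expected first events are h times that. First events per patient-month therefore equal h in each arm, a ratio of exactly 1.00. For Arm B at 50%: 0.500/4.08 = 0.123 per month in Arm B and 0.568/4.63 = 0.123 in Arm A.

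The formula in step 3 is itself the cumulative incidence of a first event with treatment failure as a competing event. A cumulative-incidence analysis of that kind returns the same 34.6%, 56.8% and 77.5%.

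**The case against.** The strongest reply is that the crude proportion is a legitimate quantity. It answers how many treated patients had a severe event under the regimen, including burden from staying on treatment longer. That stands, and it is why the crude comparison should be kept.

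No decision depends on the test. It has no stated alpha or go/no-go rule, and the stopping rule in section 16.42 counts grade 4 and grade 5 events in each arm separately. Section 16.324 also gives readers some sight of exposure. These points hold and limit the weight of the concern.

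A reader might infer that 45% v 64% makes longer observation in Arm A certain. The documents do not support that:

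- Stopping for an adverse event counts as treatment failure (section 16.11), yet section 13.2 keeps those patients in 8-weekly observation.
- Refusal is not in the failure definition, yet refusers move to event monitoring under section 13.3. A difference between arms in refusal could act in either direction.
- Section 1.4 also hypothesises better tolerance in Arm A. Holding the event hazard equal assumes that none of the gain comes from fewer adverse event stops.

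Assessment does not end abruptly either. There is a visit at progression or end of treatment, and sections 10.4 and 10.54 extend serious event and death reporting to 30 days after the last treatment. Adding 30 days lowers the excess to 2.7 to 6.2 points; counting observation-phase events raises it.

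**Conclusion.** The gap is real and modest. Section 16.325 neither defines a window nor accounts for exposure, although time on treatment and scheduled assessment depend on efficacy. Under the full design effect and an equal monthly hazard, the crude proportion is expected to be about 3 to 8 points higher in Arm A for events to 40 weeks.

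A reader might go further and conclude that an effective Arm A would look more toxic, or that the chi-square would show it. The figures do not support that. The on-treatment excess is below one standard error, and most trials would show no significant difference. Only the 104-week upper bound slightly exceeds one standard error, for Arm B incidences of about 40% to 70%.

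The result rests on assumed Arm B incidence, constant hazards, 41 treated patients per arm, and an event hazard independent of treatment failure. The last is only approximate, since an adverse event stop is itself a failure. This is a worthwhile addition to the analysis and does not threaten the trial's conclusions.

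**What to change.** In section 16.325:

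1. State the counting window for the between-arm comparison, for example on treatment plus 30 days.
2. Add a comparison of first grade 3 or higher events per patient-month at risk, with a rate ratio and confidence interval. If events cluster early, use a cause-specific hazard ratio instead, with time censored at the end of that window.
3. Keep the crude proportions and chi-square, labelled as the measure of total burden.
4. Do not substitute cumulative incidence with progression or death as a competing event, because it reproduces the same excess.

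The cost is a few lines of text and one more table. Section 18.1 already collects treatment and adverse event forms at each evaluation, and section 10.54 already requires "Grade 3 and 4 AEs regardless of attribution to the study treatment or procedure". The downside is that a constant-rate summary is approximate when the hazard changes over time; the cause-specific hazard ratio does not need a constant rate.
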